## 7.0 Study Procedures

All procedures are conducted for research purposes only. The study will be comprised of a familiarization session, an anatomical MRI brain scan session (except for those assigned to a sham group) and one experimental session. Subjects will be offered the option to combine their familiarization session and MRI scan or MRI scan and experimental session in the same day for a total of 2 lab visits or on separate days for a total of 3 lab visits. (Table 1). All study procedures will take place in the Sensorimotor Neurophysiology Lab, SPH 079 and the MRI scan will take place in the Imaging Research Facility in the Psychology building.

**Table 1.** Study structure. TMS = transcranial magnetic stimulation, cTBS = continuous theta burst stimulation, MRI = Magnetic Resonance Imaging. TMS is applied over motor cortex. cTBS is applied over DLPFC or SMG.

Session	Procedures	Proceed to next session if...
Familiarization	TMS, motor skill task, proprioception assessment	Subject comfortable with TMS, can follow task instructions, and wants to continue
MRI anatomical scan	Anatomical scan of the brain – dependent on group assignment	Subject wants to continue
Main Session	TMS, cTBS, proprioception and motor skill assessments, motor skill practice.	End of experiment

The familiarization session involves transcranial magnetic stimulation (TMS) over the motor cortex, a motor skill task that involves a series of tracing movements with the right arm, and a position sense task that involves a series of judgements about the location of their right-hand position. First, subjects will fill out a TMS screening form. Upon confirming eligibility, subjects will sit in a comfortable chair while a non-invasive brain stimulation device (the TMS coil) is held over their head. We will deliver brief magnetic stimuli over the motor cortex that evoke a small twitch in their hand muscles. Subjects will wear a pair of goggles that enable accurate positioning of the TMS coil relative to the

head (Brainsight Neuronavigation system) and have stick-on sensors on their hand to measure their muscle activity upon stimulation. This will take approximately 20 minutes.

For the motor skill task and the position sense task, they will sit in a comfortable chair and view the task display in a mirror while grasping a robotic manipulandum handle (BKIN) in their right hand (Fig. 2). During the motor skill task, they will guide a cursor representing hand position through the displayed maze. The hand feedback will be given using a visual cursor (10 mm diameter white circle). This design is similar to Mirdamadi and [name] (2020) with six straight line segments connected in abrupt corners (Fig. 2, left). Subjects will move the cursor into a red square at the start of the trial. The square will turn green after 1s, and the maze track will appear with another green square at the end of it. The participants will be instructed to reach the second target at the end of the track by moving the white cursor within the track as accurately as possible. The trial ends when the cursor enters the second target at the end of the maze. Feedback will be given about their movement time (too fast, too slow, good speed) and accuracy with points. The desired speed range will change during the speed-accuracy tradeoff assessment. The maze will be performed over three movement times (MT) ranges to assess the speed-accuracy tradeoff in three blocks of trials (MT 1: 600 – 850 ms; MT 2: 850 – 1100 ms; MT 3: 1100 – 1400 ms). 10 trials will be performed in each MT range and the block order will be randomized. The maze tracing will be standardized meaning the same maze will be used for all the trials between subjects.

During the position sense task, the participant's hand will be passively moved by the robotic manipulandum to two different positions. Participants will be asked to report whether the second position is closer to their body than the first position. An adaptive staircase algorithm is used to determine the test positions with a 0.5 cm step size. There will be 82 trials in total each time and the test will be standardized across participants.

The motor skill and position sense assessments will take approximately 30 minutes. If subjects are comfortable with all procedures and can follow task instructions, they will be assigned to a group. This group assignment will decide whether they need an anatomical brain scan.

[figure not shown]

Figure 2. Setup for behavioral procedures. Participant holds handle of robotic manipulandum with right hand and makes arm movements to targets presented in visual display (motor skill task) or judges where handle is moved in relation to a target (position sense task).

primary motor cortex with TMS (Caulfield et al., 2022; Nieminen et al., 2022). The main session includes all the same elements as the familiarization session (TMS, proprioceptive assessment, motor skill task), plus cTBS. After the first motor skill assessment and proprioception assessment (Fig. 1), we will deliver single pulses of magnetic stimuli over the motor cortex and determine the resting motor threshold (RMT) as the lowest TMS intensity that elicits a muscle twitch of at least 50 microvolts at least 10 times out of 20 (Rossini et al., 2015). We will then deliver cTBS in the standard pattern (600 pulses over 40 seconds, at an intensity of 70% of RMT). For non-sham groups the coil will be positioned over DLPFC or SMG, as determined by the Brainsight neuronavigation system. For sham groups, the coil will be tilted 90 degrees so the magnetic field is not directed into the head; they hear the clicking noises but no current is induced in the brain (Rossi et al., 2009). Then, subjects will perform second pair of assessment tasks. This will be followed by practice of the maze tracing task for about 20 minutes, with a motor skill assessment partway through. Practice of the maze task will occur at a single MT range (MT 2). The session will conclude with the third pair of assessment tasks.

## 8.0 Study Calendar

	Familiarization Session	MRI session if needed	Main Session
	First visit	Second visit	Second or third visit
STUDY PROCEDURES			
In person screen, Consent and Handedness questionnaire	X		
TMS tolerance check	X		
Practice Behavioral tasks	X		
Random group assignment	X		
In person Screening		X	X
cTBS			X
Position sense assessment task			X
Motor skill assessment task			X

	Familiarization Session	MRI session if needed	Main Session
	First visit	Second visit	Second or third visit
Motor skill practice			X

## 9.0 Reportable Events

Outcome and Adverse Event Data including: seizure induction (rare), syncope (epiphenomenon); transient headache, neck pain, toothache, paresthesia, hearing changes; lightheadedness; and nausea (Rossi et al., 2009).

Expected adverse events that will be reported in annual reviews:

1. Slight discomfort lasting less than a second on the scalp near the TMS coil.
2. Twitching of the face and jaw due to the magnetic pulse, which may be unpleasant but usually not painful.
3. Transient headache, neck pain, toothache, paresthesia, hearing changes.
4. Lightheadedness or nausea

Exceptional adverse events that will be reported immediately:

1. Seizure. The appearance of a seizure during application of TMS with stimulation parameters regarded as safe cannot be excluded, therefore we defined appearance of a seizure as an exceptional adverse event.
2. Syncope.

All exceptional adverse events will be reported to the IRB immediately by the PI. Subjects will be excluded for seizure induction and syncope. However, the subject will make the decision for continuation for the other transient discomforts.

In addition to the IRB's minimal requirements, we will report adverse events including: date, time, description of the adverse event, and treatment or handling of the event. We will also provide a summary of cumulative adverse events annually.

## 10.0 Data Safety Monitoring

The PI will be responsible for data and safety monitoring. The study team will meet at least monthly to discuss any difficulties with carrying out the experimental protocol and to review the data. [name] will always be available in person or by phone when data collections are occurring. Notes recording the date of each meeting and the results of the safety review will be kept in the [name] lab's Teams channel for this project.

## 11.0 Study Withdrawal/Discontinuation

The participant will contact the study personnel by phone or e-mail and inform us that he or she is withdrawing. There are no risks to participant by withdrawing early. If an exceptional adverse event occurs, we will withdraw the subject immediately. For minor, expected adverse events, withdrawal will be discussed with the subject. We would also withdraw the subject if they are unable to follow the instructions for the motor skill task or position sense task. If a subject meets exclusion criteria temporarily on their familiarization session and/or first experimental session (e.g., did not get more than 4 hours of sleep the night before, drank too much coffee, etc), we will simply reschedule the session. However, if they temporarily meet the exclusion criteria on their second experimental session, they will be excluded. If the subject develops a medical condition such that they no longer pass the TMS screening questionnaire and the situation is not temporary, we will withdraw the subject. Participants may also be excluded if we are unable to make the TMS measurements. This happens on rare occasions

when we can't identify a good motor hotspot to deliver the stimuli. In any case, we would pay any withdrawn participant for the amount of time they have spent participating.

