## 2.0 Objective(s)

The aim of the present study is to test role of activity in SMG and DLPFC in proprioception and motor skill learning. A robust way to identify whether a brain region plays a role in a behavior is to temporarily modulate its excitability in healthy people using non-invasive brain stimulation

(Cohen et al., 1997; Reis et al., 2008). This is commonly done in research with a short sequence of low-intensity transcranial magnetic stimulation (TMS), also known as repetitive TMS (rTMS). A small, temporary reduction in cortical excitability can be achieved through continuous theta burst stimulation (cTBS), a low intensity patterned form of rTMS that is delivered over 40 seconds, with excitability effects lasting up to an hour (Huang et al., 2005). rTMS is used clinically to treat conditions such as depression and is considered very low risk provided the generally accepted screening criteria are met. In the research setting, this technique is widely used not only in healthy adults (as in this study) but also in children and people with concussion, stroke, Parkinson's disease, and more (Rossi et al. 2021).

In separate groups of subjects, we will use a 40-second sequence of rTMS called continuous theta burst stimulation (cTBS) over SMG, DLPFC, or sham (control), before the subject performs tasks known to involve proprioception and either a short or longer sequence of motor skill learning (a maze tracing task). If cTBS over SMG or DLPFC has an impact on task performance for that group (in comparison to the sham, or control group), it suggests activity in that brain region is important for the affected aspect of task performance.

This project has two objectives:

- Objective 1. To explore the role of DLPFC and SMG in proprioception.
- Objective 2. To assess the role of DLPFC and SMG on motor skill learning and proprioceptive changes at two different time scales.

[figure not shown]
Because cTBS is intended to be disruptive, it is possible that the sham group will have the best performance in one or more outcome measures. It is also possible that some aspects of performance will be better in the SMG or DLPFC group due to complexities of the neural networks supporting these behaviors. However, it is not the goal of the study to determine which intervention yields the “best” task performance, it is simply to determine the details of how the DLPFC and SMG groups differ from each other and from the sham group.

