- Claustrophobic, or are unable to remain still for long periods of time; or use an intra-uterine device (IUD) who's MR compatibility has not been established.
- People who have a BMI over 30 will be excluded as it may be uncomfortable or impossible to lay in the MRI scanner.
- Potential subjects will be invited to reschedule if they would otherwise be eligible (according to the initial screening), but the day of testing have drunk more than 3 units of alcohol or taken other recreational drugs in the 24 hour period prior to testing; have had more than 3 cups of coffee in the last hour; are sleep deprived (<4 hours sleep the previous night); or have participated in another brain stimulation experiment the same day.
- In addition, we will invite subjects to reschedule if they have any of the common Covid symptoms within the last week.
- After giving their consent, participants may be excluded during or after the familiarization session if they are unable to perform the reaching task or follow instructions, or if their TMS stimulation parameters cannot be reliably determined by the experimenter, or if TMS is not well tolerated.

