## 5.0 Study Design

## 6.0 Enrollment/Randomization

Potential subjects will initiate contact with the research staff in response to the recruitment flyers. The subject will be given information about what the experiment entails and will be asked questions to make sure they meet the inclusion/exclusion criteria. If they are interested in participating and meet the inclusion/exclusion criteria, then they will be scheduled for their first session (familiarization session) which will take place in the Sensorimotor Neurophysiology Laboratory, [name].

At the familiarization session, before any experimental procedures occur, a research team member will explain the procedures in more detail and go through the consent form with the subject. The subject will then have the opportunity to ask any questions and read the informed consent before signing. After the familiarization session, if the subject was not bothered by TMS and wants to continue, random group assignment will occur, following a block randomization table. There will be 3 groups that differ in cTBS intervention and amount of motor skill practice. Subjects will have a 67% chance of receiving cTBS, and a 33% chance of receiving sham cTBS (details below).

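### The task-inability withdrawal rule has no time limit and no analysis set is defined, so outcome-related losses after assignment and cTBS could bias the active-versus-sham comparison

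*Combined protocol and SAP*

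**What the plan says.** Section 11 sets the rule: "We would also withdraw the subject if they are unable to follow the instructions for the motor skill task or position sense task". It names no session and no cut-off in time. Section 4.2 has a parallel rule, under which "participants may be excluded during or after the familiarization session if they are unable to perform the reaching task or follow instructions".

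The order of events is clear. In Section 7 task ability is checked first: "If subjects are comfortable with all procedures and can follow task instructions, they will be assigned to a group". Table 1 makes the same check a condition for leaving the familiarization session. Section 6 then states that "random group assignment will occur, following a block randomization table". cTBS comes later, in the main session, and afterwards both tasks are repeated: "Then, subjects will perform second pair of assessment tasks". Section 3 defines the two outcome measures from these tasks, with proprioception assessed three times and motor skill four times.

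Section 2 gives the expected direction: "Because cTBS is intended to be disruptive, it is possible that the sham group will have the best performance". It adds that active groups might do better on some measures, and it describes the excitability effect as small and temporary.

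Section 12 gives f = 0.14, 24 per group, 0.8 power, alpha 0.05 and a mixed measures ANOVA. It gives no analysis set, missing-data rule, replacement rule or dropout allowance. The only consequence of withdrawal that Section 11 states is payment for time spent.

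**The concern.** The pre-assignment check already removes people who cannot do the tasks. What an open-ended rule adds is withdrawal later on, including after cTBS. At that point the judgement rests on behaviour in the tasks that are the outcome, after an intervention expected to alter that behaviour. Withdrawals made then can be related both to arm and to outcome, and randomization no longer protects a comparison among those who remain.

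Two features make this more than a formality. First, no written criterion separates failing to follow instructions from performing very badly, for example by repeatedly missing the movement-time window. No section describes blinding of whoever makes the call, and in Section 7 sham is given by tilting the coil 90 degrees. Second, a repeated-measures ANOVA ordinarily needs every timepoint, so a participant stopped partway would fall out of the analysis by default, along with the assessments already recorded.

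**Working it through.** **1. The plan's own figure.** Inputs from Section 12: f = 0.14, alpha 0.05, power 0.8, 24 per group. For a within-between interaction, lambda = f² × N × m / (1 − rho), df1 = (g − 1)(m − 1), df2 = (N − g)(m − 1). The documents give no rho; 0.5 is assumed.

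- g = 6 cells (3 stimulation types × 2 training durations), m = 3, N = 144: lambda = 0.0196 × 144 × 3 / 0.5 = 16.9 and power = 0.804. The figure of 24 reproduces.
- g = 3, m = 3, rho = 0.5: power at 24 per group is 0.616, and 35 per group would be needed. With g = 3, m = 4, rho = 0.6, 24 per group reproduces again (0.802).

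Section 6 speaks of three groups, so which reading was used is open. That is a separate matter. No reading includes an allowance for withdrawals.

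**2. What f = 0.14 means as a group shift.** Section 12 attaches f to an interaction that includes timepoint. Assume three groups, three timepoints, f as the SD of the interaction effects over the common SD, and one group shifted by delta at both post-cTBS timepoints.

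- Centred group pattern: (2/3, −1/3, −1/3), sum of squares 2/3. Centred time pattern: (−2/3, 1/3, 1/3), sum of squares 2/3.
- Interaction sum of squares = delta² × 2/3 × 2/3 = 4 delta²/9. Over nine cells this is 4 delta²/81, so f = 2 delta/9.
- delta = 0.14 × 9/2 = 0.63 SD.

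**3. Worst-case loss from one active arm.** Assume a normal outcome, loss of exactly the lowest scorers, all from one arm of 24, and the same people lowest at both post-cTBS timepoints. The three lowest expected values in a sample of 24 standard normals are −1.948, −1.503 and −1.239.

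| Lost | Shift in the mean (SD) | Share of 0.63 SD |
|---|---|---|
| 1 | 1.948/23 = 0.085 | 13% |
| 2 | 3.451/22 = 0.157 | 25% |
| 3 | 4.690/21 = 0.223 | 35% |

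These shares assume that baseline is unrelated to the post-cTBS score. With correlation rho, the baseline mean rises too and the net share is multiplied by (1 − rho). At rho = 0.5 it is about 7%, 12% and 18%.

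**4. A milder model: one performance cut-off for all arms.** Assume a true post-cTBS deficit d = 0.5 SD. With a fraction q of the active arm removed and z the q-quantile of the standard normal, the active mean becomes −d + φ(z)/(1 − q). The sham mean becomes φ(c)/(1 − Φ(c)), with c = z − d. For q = 5%: active −0.5 + 0.109 = −0.391; sham +0.041; difference 0.432, or 86% of the true effect.

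| Active removed | Sham removed | Effect kept | Power at N = 144 if f shrinks in proportion |
|---|---|---|---|
| 2% | 0.5% | 93% | 0.73 |
| 5% | 1.6% | 86% | 0.65 |
| 10% | 3.7% | 78% | 0.54 |

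**5. Direction.** If cTBS improves performance by 0.5 SD and 5% of sham falls below a common cut-off, 86% of the effect is kept, so it still shrinks. If there is no true effect and only the active arm loses its lowest 5%, the active mean rises by 0.109, a false difference of about 0.11 SD in favour of active. With no post-cTBS withdrawals the bias is zero.

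**The case against.** The strongest reply is that the trigger is failure to follow instructions, not a poor score. A participant disrupted by cTBS would still trace the maze and still answer the position question, and would simply score worse. Everyone assigned has already shown that they can do the tasks, and Section 2 calls the excitability effect small. This stands as far as it goes. A reader might infer that the rule removes the most affected participants; the documents do not show that. They show only that nothing prevents it, since the check precedes cTBS and no criterion marks off inability from very poor performance.

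The parallel wording in Section 4.2 may be meant only for the familiarization check, where Table 1 places it. That is a fair reading, but the Section 11 sentence carries the point without it.

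It is also true that nothing says recorded data are discarded. The loss follows from the usual behaviour of the planned ANOVA and the absence of an analysis set, not from a stated rule.

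On size, one might convert f = 0.14 as if for a one-way comparison of three groups (0.14 × 3/√2 = 0.297 SD) and conclude that losing 1 to 3 participants cancels 29% to 75% of the effect. Section 12 states f for an interaction with timepoint, so that conversion does not apply. On direction, bias toward no effect is not certain, as the last working step shows.

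Finally, Section 11 excludes participants who are temporarily ineligible at a second experimental session. Because sham participants skip the MRI visit, a reader might infer that this falls on active arms only. Section 7 names the MRI apart from the one experimental session, so that reading is strained. The criteria concerned, such as sleep and coffee, also have nothing to do with performance after cTBS.

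**Conclusion.** The concern holds in limited form. As written, the rule permits outcome-related withdrawal after assignment and after cTBS, and neither an analysis set nor a missing-data rule protects the comparison. The likely bias is toward no effect; a false difference is possible if losses concentrate in one arm.

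The size cannot be fixed from the documents. It may be zero. The 13% to 35% range is an upper illustration that rests on the assumptions in steps 2 and 3: only the lowest scorers lost, all from one arm, and no correlation with baseline. If the effect is meant to differ by training duration as well, the implied shift exceeds 0.63 SD and the shares are smaller. This should be corrected because the gap is easy to close before data are seen and hard to defend afterwards.

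The second-session sentence is a real but secondary contradiction with Sections 4.2 and 7.

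**What to change.** - In Sections 4.2 and 11, state that task inability excludes a participant from the study and the analysis only up to random assignment, where Table 1 already checks it. Withdrawal for adverse events or at the participant's wish is not affected.
- In Section 12, define the analysis set as all participants who received real or sham cTBS, in their assigned group, with every recorded assessment whatever the performance. Use a mixed model in place of the ANOVA so that partial sessions contribute.
- Report non-completers by group, with reasons.
- If an assessment yields no interpretable psychometric function, treat that assessment as missing and report the count by group.
- Separately, reconcile the Section 11 sentence, "if they temporarily meet the exclusion criteria on their second experimental session, they will be excluded", with the single experimental session in Section 7 and with the rescheduling rule in Section 4.2.

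The cost is wording and a change of model. A few noisy records stay in and some assessments may be unusable. The stated 24 per group does not change.
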